**Table 1: EMA application sample questions.**

Forms	Behavior Domains	Questions
Daily	Smoking, Diet/Alcohol Use, Sexual Activity	Did you smoke today/this week? (yes/no) If so, how many items did you smoke today? (#); Did you eat any vegetables today/this week? (yes/no); Did you use any alcohol today/this week? (yes/no); Did you have any sex with anyone who was not your marital or long-term partner today/this week? (yes/no) If so, did you use condoms? (yes/no)
Random		
Weekly		
Event-contingent	Smoking, Diet/Alcohol Use, Sexual Activity	Checklist Format: Within the past hour, I smoked, ate vegetables, drank alcohol and/or had sex with someone who was not my marital or long-term partner.

In response to data entered by participants, the EMAI application will be programmed with algorithms to provide real-time feedback, i.e. EMI, through tailored health text messages. Only patients randomized to the EMI arm will receive these messages. We will use general health as well as behavior-specific messaging. Examples are shown in Table 2.

**Table 2: Examples of EMI responses.**

EMA Data Collected	EMI Response
Any “negative” health behavior entered.	“Today is a great day to start being healthy.” “You can make a difference in your health.” “You have people around you who care about you.”
Did you eat any vegetables? NO	“Eating a mixed diet (meats and vegetables) is a healthy way to go.”
Participant enters a geolocation previously associated with smoking.	“There are better things to spend money on than cigarettes.” “Smoking causes lung cancer.”

*Cultural Adaption, Language, and Literacy Formative Work.* Prior to beginning formal recruitment, we will test the appropriateness of our questions and messaging in terms of cultural adaptation, clarity, and meeting literacy requirements. Specifically, we will use our initial list of proposed questions and messages and then ask potential participants (~10) in the study whether the questions and messaging are clear, acceptable, and correctly understood by them. We will then refine questions and messaging as needed.

**Secondary Objective: To assess processes, facilitators, and barriers to EMAI-**These results will inform future EMAI implementation, scale-up, and sustainability questions. We will utilize a mixed methods (quantitative and qualitative) approach involving process indicator analyses, in-depth interviews (IDI), and focus group discussions (FGD).

Quantitative Methods and Analytic Plan for Process Measures. We will gather process data during EMAI implementation to include: *EMA prompt response rate, form completion rates, out-of-network time, malfunctions, down time, and device retention.* Process measures analyses will be exploratory in nature. We will use descriptive statistics, as well as explore associations with moderating/mediating

Date: March 30, 2015  
 Principal Investigator: [name], MPH  
 Application Number: IRB00065934

factors such as gender and age using Chi-square, Fisher’s exact test, and multivariate regression methods as appropriate.

**Qualitative Methods. Study Population.** All participants will take part in IDIs (n=120) which will explore individual experiences with the EMAI application. IDIs will occur immediately after completion of the 90 day follow-up period. Smaller groups (6-8 each) will participate in 2 FGDs after Day 30 and Day 90 of the study (4 FGDs total, ~24-32 participants total) to create a more dynamic and interactive forum for additional insights. **Data Collection.** RHSP has an experienced Qualitative Research Department to help ensure high quality data collection. Semi-structured interview guides will be used for qualitative data collection with open-ended questions on EMAI processes, barriers, facilitators, confidentiality, satisfaction, challenges, suggestions for improvement, and perceived effect of EMI on behaviors. We will also explore issues regarding long-term adoption of this type of technology, gender-specific considerations, and how EMAI is or is not integrated in relation to current everyday use of mobile phones in this setting. All IDIs and FGDs will be conducted in the participants’ preferred language and digitally recorded. Translation and transcription will be done in a single step by trained staff. **Analytic Plan.** Data will be entered into ATLAS.ti software (GmbH, Germany) to facilitate coding and analysis. Following an iterative approach, transcript review will begin while IDIs and FGDs are still underway and participant responses will be used to shape questions for future interviews. Initial line-by-line coding will be completed on a sample of transcripts to develop a codebook, which will then be used to categorize responses into thematic categories. Quotes from coded transcripts will be triangulated with the original transcripts to ensure appropriate contextualization. The study team will meet and discuss identified themes and come to consensus on what modifications, if any, need to be incorporated into the EMAI application in future iterations. These modifications will be carefully documented.

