#### 4. Study Procedures

##### **Primary Objective: To conduct a pilot EMAI study with smartphones in Rakai, Uganda.**

**Study design.** This pilot study will be nested within the Rakai Community Cohort Study (RCCS, WIRB #20031318), an ongoing, population-based, prospective, observational study which surveys Rakai District communities in Uganda every ~12-18 months.

**Study setting and population.** Rakai District (~2200 km^2) is a mostly rural district (population~400,000) in Uganda bordered by Tanzania and Lake Victoria. RHSP has been conducting community-based research in Rakai since 1988 including large, prospective health behavior studies. RHSP survey results of demographic and behavioral characteristics are similar to those reported for southwestern Uganda in Demographic and Health Surveys, suggesting that despite long-term surveillance and health education, the population is typical of rural/semi-rural Uganda.

**Rakai Community Cohort Study (RCCS):** RHSP's ongoing 54 community (n~20,000) longitudinal HIV surveillance study provides >20 years of data on HIV prevalence/incidence, health behaviors, sexual networks, and mobility/migration in Rakai District, Uganda.

**Eligibility.** We will aim to recruit 120 total adults (age  $\geq 18$  years) from current, literate RCCS study participants. We will purposely recruit a sample that has a broad range of participant characteristics in our study to optimize diversity of responses and increase study generalizability. Specific variables for which we will target sampling include: gender (~50% female), age (at least 20% among age groups 18-25, 26-35, >50), and occupation (at least 20% traders and farmers).

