**Recruitment.** As part of a detailed written informed procedure, RCCS participants have consented to be contacted for future studies. We will enumerate a list of current RCCS participants with key demographics, and, as described above, we will purposely select participants meeting our study population composition goals. We will begin with recruitment via RCCS in locations where it is actively conducting its continual surveys of the Rakai community, asking participants as they undergo the RCCS survey if they would also like to participate in this nested study. If we are unable to conveniently obtain our desired sample via ongoing survey activities of RCCS, we will send trained staff to recruit RCCS participants from communities in which RCCS has recently conducted surveys. Eligible participants will be asked to complete a written informed consent procedure (see Section 8 below) in order to enter this specific study.

**Participant-related Procedures.** *Participant training.* After recruitment, participants will undergo a ~30-60 minute training session. A brief training curriculum will be used consisting of basic phone use,

Date: March 30, 2015

Principal Investigator: [name], MPH

Application Number: IRB00065934

contacting the study team, and detailed instruction on EMAI application use. Participants will be required to demonstrate proficiency with the EMAI interface prior to receiving a study smartphone. The first 48 hours after the participant has the phone will be a “run-in” period to allow for troubleshooting of device problems and to allow participants to become familiar with the EMAI application procedures.

*Follow-up (Days 1-30, Baseline Behaviors).* After the run-in period, all participants will receive assessment questions only for a 30 day period in order to establish baseline behaviors. After completing this initial 30 day period, participants will be required to return to the study office to complete a short questionnaire (see Aim 3) and to be randomized to the second phase of follow-up.

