Protection of confidentiality: *Research materials:* Materials will include the interviews, consent forms, and mobile phone logs of all activity conducted through the mHealth application. In order to preserve confidentiality, informed consent documents – which by definition include the participant's name - are retained in locked filing cabinets and secure store rooms, accessible only to senior investigators or designated staff. No personal identifiers will be attached to the questionnaire or samples. Electronic data sets and clinical readouts are downloaded into password protected computers, and individual identifiers are stripped. Names linked to study IDs are stored in a separate, password protected electronic file, on a computer and server accessible only to authorized senior personnel. All RHSP research staff have received extensive human subjects/research ethics training, including the need for complete confidentiality. Participant entered EMAI data will be encrypted at all times, be it on the phone, with data transfer, or sitting on the server. The application and server access will be password protected. If a phone is lost or stolen, we will have the ability to remotely wipe the phone of all data and render it inoperable. All interviews will be conducted in private or, if appropriate, as a focus group. If a breach of confidentiality occurs, we will report to the appropriate IRBs according to NIH guidelines. The principal investigator will discuss any breaches of confidentiality and intervene as necessary to decrease the risk of future breaches.

Avoidance of social harm: We will counsel participants on the need to be discrete with their smartphones to avoid risk of being targeted for theft or exploitation. We will attempt to use locally available smartphones to minimize the novelty of participants using these devices. We will teach participants to immediately contact study staff if they have any negative experiences and they will be able to return the phones and quit the study at any time.

Date: March 30, 2015  
Principal Investigator: [name], MPH  
Application Number: IRB00065934

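### Every individual interview is timed after Day 90 and no exit interview is described, so the reasons of early leavers will be under-represented in the barriers objective

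*Combined protocol and SAP*

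**What the plan says.** One secondary objective (Section 2) is to learn what helps and what hinders EMAI. Section 4 serves it with three methods: process indicators, in-depth interviews (IDIs) and focus group discussions (FGDs).

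- **Interviews.** Section 4, Qualitative Methods: "All participants will take part in IDIs (n=120"), and "IDIs will occur immediately after completion of the 90 day follow-up period".
- **Focus groups.** Same paragraph: groups of 6 to 8 "will participate in 2 FGDs after Day 30 and Day 90 of the study (4 FGDs total, ~24-32 participants total"). The guides, which serve interviews and groups alike, contain "open-ended questions on EMAI processes, barriers, facilitators, confidentiality, satisfaction, challenges, suggestions for improvement".
- **Process indicators.** Section 4: "EMA prompt response rate, form completion rates, out-of-network time, malfunctions, down time, and device retention". Staff also log every phone malfunction.
- **Questionnaires.** Satisfaction and acceptability are asked at Days 30, 60 and 90.
- **Leaving.** Section 8, Avoidance of social harm: "they will be able to return the phones and quit the study at any time". The right to withdraw is repeated in the paragraph on discomfort and fatigue.
- **Phone loss.** Section 4: no replacement phone and no incentive, but the participant is kept in the analyses.
- **Entry.** Section 4, Participant training: "Participants will be required to demonstrate proficiency with the EMAI interface prior to receiving a study smartphone". What happens to someone who does not reach proficiency is not stated.

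No interview or questionnaire at withdrawal is described anywhere.

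**The concern.** The interview is the only qualitative instrument meant for everyone, and its timing is tied to the end of follow-up. People who leave because of fear of theft, loss of privacy, fatigue or trouble with the device are the ones best able to describe a barrier strong enough to end use. Under the plan as written, nobody is scheduled to ask them individually. Section 4 says the results of this objective are to guide later implementation and scale-up, so a gap in the reasons for leaving would carry into the design of the larger trials.

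Payment may add to the selection. Section 10 pays incentives after each questionnaire and withdraws them below 80% of prompts, and Section 4 withdraws them after loss or theft. Some of those with the most difficulty therefore have less reason to come back to the office at Day 90.

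**Working it through.** **1. The plan's own counts.** Four FGDs of 6 to 8 people give 4 × 6 = 24 to 4 × 8 = 32, as stated. The 120 interviews equal the recruitment target of 120 in Section 4 (Eligibility). Interviews held at Day 90 = 120 × (1 − d), where d is the proportion leaving before then, so 120 requires d = 0.

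**2. Interviews under attrition.** The documents give no rate, so d is assumed.

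| d (assumed) | Leavers | Interviews after Day 90 |
|---|---|---|
| 5% | 6 | 114 |
| 10% | 12 | 108 |
| 20% | 24 | 96 |
| 30% | 36 | 84 |

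**3. What reaches a leaver, by time of leaving.**

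| Leaves | Interview | Focus group | Questionnaire | Process indicators |
|---|---|---|---|---|
| Before Day 30 | none | none | none | until exit |
| Between Days 30 and 60 | none | Day 30, if chosen | Day 30 | until exit |
| Between Days 60 and 90 | none | Day 30, if chosen | Days 30 and 60 | until exit |

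A questionnaire answered before someone decides to leave may record dissatisfaction, but it is not an account of why they left.

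**4. How much the Day 30 focus groups can add.** They hold 2 × 6 = 12 to 2 × 8 = 16 people, which is 12/120 = 10% to 16/120 = 13% of the target. No selection rule is given. Assume random choice, and that half of all leavers go after Day 30. With k later leavers among N people still enrolled at Day 30 and m group members, the expected number of later leavers in the groups is mk/N. The chance of at least one is 1 − C(N−k, m)/C(N, m).

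| d | k | N | Expected, m = 12 to 16 | Chance of at least one |
|---|---|---|---|---|
| 10% | 6 | 114 | 0.63 to 0.84 | 50% to 61% |
| 20% | 12 | 108 | 1.33 to 1.78 | 78% to 87% |

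These groups come at the close of the assessment-only phase (Days 1–30), so they can say little about barriers to the intervention messages.

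**5. Process indicators.** Response rates, down time and device retention are gathered during implementation and are not confined to completers. They show when use fell or stopped, and the malfunction log can explain technical failures. They would not record a worry about theft or privacy.

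**The case against.** The best defence is that the interviews are one of three methods. Two of the four focus groups follow Day 30 and use guides that cover barriers, process data cover everyone with a phone, and acceptability is asked at Days 30 and 60. Participants are also told to contact staff at once about bad experiences. Adverse events are recorded, and the principal investigator reviews intervention acceptance quarterly. The interview sentence names all participants, so the 90-day period could be read as calendar time. The study is an exploratory pilot.

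Much of this stands and limits the point. A reader might infer that the barriers objective is answered only by people for whom EMAI worked. The documents do not support that: a poor responder, or someone with a failing phone, who reaches Day 90 is still due an interview. Nor do they support a claim that feasibility is biased upward, since retention and response measures count failures among those who leave.

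A reader might also infer that people who fail the proficiency check are excluded from all data. The protocol is silent on them and places training after recruitment. The supportable statement is that their handling is unspecified.

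The defence does not close the gap. No planned interview, group or questionnaire reaches someone who leaves before Day 30. Spontaneous contact with staff is not a structured account of reasons. The calendar reading would need a procedure for contacting people who have withdrawn, and none is described.

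**Conclusion.** The point holds in a limited form. Individual interviews make no provision for early leavers, the figure of 120 assumes no attrition, and reasons for leaving will be under-represented. The other sources offset this only in part.

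The count of missing interviews is simple arithmetic on an assumed rate: 6 to 36 of 120 at 5% to 30% leaving. The effect on the findings cannot be sized. It is tempting to turn the gap into a prevalence error, even to say that half of all barriers would be missed, but any such figure comes from the inputs chosen. If a barrier affected 60% of leavers and 20% of completers, completers alone would understate it by d × 40 points, which is 4 points at 10% leaving and 8 at 20%. With 50% and 30% the gap is d × 20 points, or 2 and 4. All four rates are assumed, and the interviews are open-ended and coded into themes, with no prevalence estimate planned. No power or sample size figure in Section 7 is affected.

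This is a worthwhile low-cost improvement to a secondary objective. It rests on the change of interview timing. The missing recruitment and proficiency counts are a minor addition and would not carry the point alone.

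**What to change.** In Section 4, Qualitative Methods, time the interview at Day 90 or at withdrawal or early phone return, whichever comes first. Offer the acceptability questions at the same contact if the participant agrees. Participants whose phone is lost or stolen, who stay in the analyses, should be offered the interview even if they do not return at Day 90. Participation at exit must be optional, in keeping with the right to withdraw without adverse consequences. Replace the fixed figure of 120 with a report of interviews completed against all enrolled, separately for those who left early and those who did not.

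As a minor addition, keep an aggregate count of people approached, declining, failing proficiency and not reaching Day 30. A count is enough; no individual data on decliners are needed.

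**Cost.** The number of planned interviews does not rise; some are held earlier, and staff need a short exit procedure and a tally. Some leavers will refuse, so coverage will be partial. Reported acceptability may look less favourable.

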**Secondary Objective: To compare EMAI-collected with traditional questionnaire-collected data-**  
 We will describe and compare EMAI versus traditional questionnaire-collected data.

**Methods.** All study participants will be administered a traditional paper-based questionnaire at the completion of the 30 day follow-up period and a similar questionnaire after the 60 and 90 day follow-up periods. This questionnaire will assess satisfaction and acceptability of the participant’s experience using EMAI. Additionally, the questionnaire will ask the same behavioral questions as the EMAI application, but ask participants to recall these behaviors over the past 30 days, e.g. over the past 30 days, how many days did you drink alcohol?

**Analytic Plan.** Responses to traditional questionnaire data will be compared with EMAI collected data using descriptive statistics such as percent agreement, Kappa statistic, scatter plot correlation graphs, mean within-pair differences, coefficient of variation, and Bland-Altman plots. Successful completion of this aim will generate important preliminary evidence on EMAI acceptability and reliability to support future NIH studies.

**Timeline for proposed study.**

Activity	Study Month→	1-2	3-4	5-6	6-7	7-8	9-10	11-12	13-14	15-16	17-18	19-20	21-22	23-24
Formative work on messaging														
mHealth EMAI Software Programming and Testing														
EMAI Recruitment and Implementation (90 days total per participant, follow-up periods will be asynchronous)														
Mixed Methods Evaluations														
Final Analyses and Dissemination														

- 5. **Inclusion/Exclusion Criteria**-See above.
- 6. **Drugs/ Substances/ Devices**-Not applicable.
- 7. **Study Statistics (for Primary Objective)**

**Sample Size/Power Calculations.** This is an exploratory study powered not to assess intervention efficacy but to provide preliminary estimates of effect. As an example, Table 3 shows power calculations for alcohol use based on different estimates of intervention impact. Prior data indicate that approximately 50% of the Rakai population uses alcohol on a weekly basis. If there is a 50% reduction in alcohol use following EMAI, the study will have 81.5% percent power to detect this difference.

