# Mobile Behavioral Ecological Momentary Assessment and Intervention in Rakai, Uganda: A Pilot Study

## 1. Abstract

Ecological Momentary Assessment and Intervention (EMAI) is an emerging technique for gathering richer and more relevant data through repeated, longitudinal sampling of participants in their natural setting in order to deliver real-time interventions. Challenges with instilling healthy behaviors are well documented. These challenges are magnified in low and middle income countries (LMICs) where significant social and structural barriers to care often exist. The rapid emergence of mHealth (mobile technologies for health), including growing access to low-cost smartphones, now allows for unprecedented advancements in and novel research on mHealth applications in LMICs. We therefore propose a pilot EMAI study of health behavior in Rakai, Uganda.

This study aims to demonstrate that it is feasible and acceptable to use smartphones in a LMIC to collect near real-time, geolocated behavioral information and to send tailored health messages based upon this data. This proposal will provide unique insights into the geospatial/temporal epidemiology of health behaviors, generate preliminary estimates of intervention impact, and establish an evidence-base for future large-scale, randomized EMAI mHealth trials. This study will be nested within the Rakai Health Sciences Program's (RHSP) ongoing Rakai Community Cohort Study (RCCS).

Our main study objective is to conduct a pilot EMAI study among current RCCS study participants. Participants will be given a smartphone with an application that will collect GPS-based geolocations and ask assessment questions (e.g. diet/alcohol, smoking, and sexual behaviors). Using participants' responses, the application can deliver tailored intervention health messaging to participants using pre-programmed algorithms. During Days 1-30 of follow-up, all participants will receive assessment questions only to establish baseline behaviors. During Days 31-90, participants will be randomized to either continuing with assessment questions only (control arm) or to also begin receiving intervention messaging (intervention arm). The randomized design will allow for calculation of an estimate of EMAI effect on diet/alcohol, smoking, and sexual behaviors which will be used to design future, large-scale randomized controlled trials of EMAI.

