**A disease and prevention/treatment agnostic EMAI platform could be highly scalable.** This study proposes to test a disease and prevention/treatment agnostic EMAI platform. We will test this platform by targeting three behavioral areas of high public health significance, i.e. smoking, diet/alcohol, and sexual activity, which contribute to smoking-related cancers, obesity, and HIV transmission. This agnostic platform could be adapted for most health care conditions, making it highly scalable and increasing potential impact.

**Preliminary studies.** Our group has done extensive and pioneering work in mHealth (including EMAI), mixed methods research, and longitudinal surveillance of health behaviors. *emocha*-We have experience in the design, development, implementation, and evaluation of mHealth as founders of *emocha*, an mHealth software platform. We have conducted a number of EMAI studies domestically, including The EXposure Assessment in Current Time (EXACT) study (5U01DA023832; PI: [name]) assessed drug use and psychosocial stress in injection drug users (IDUs) in urban Baltimore. We developed a EMA application for this study which was successfully implemented with excellent participant response and demonstrated validity. Another EMAI application developed by

Date: March 30, 2015  
Principal Investigator: [name], MPH  
Application Number: IRB00065934

our group to assess HIV care engagement (clinic attendance and adherence), drug cravings, and psychosocial stress to improve retention in care and adherence to medications for out-of-care, HIV-infected IDUs has also been successfully implemented (R34DA033181; PIs: [name], [name]). Finally, we have developed an EMA application to assess alcohol use and sexual behaviors in men who have sex with men in Baltimore which successfully recruited participants (P30AI094189; PI: [name]).

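### Does the pilot need planning rates or recruitment minimums for smoking and sexual behaviour, when Section 7 quantifies only alcohol?

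*Combined protocol and SAP*

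**What the plan says.** The Abstract says that the randomised design will yield "an estimate of EMAI effect on diet/alcohol, smoking, and sexual behaviors which will be used to design future, large-scale randomized controlled trials". Section 3 (Background) likewise describes the platform test as "targeting three behavioral areas of high public health significance, i.e. smoking, diet/alcohol, and sexual activity".

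Section 7 (Sample Size/Power Calculations) calls the study exploratory. It says that the study is not powered for efficacy and is meant to give preliminary effect estimates. It then continues: "As an example, Table 3 shows power calculations for alcohol use". The planning rate is that "approximately 50% of the Rakai population uses alcohol on a weekly basis". Table 3 gives power of 0.195, 0.381, 0.611 and 0.815 for reductions of 20, 30, 40 and 50%. No rate is given for smoking, vegetable intake or sex outside a long-term partnership.

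Section 4 (Eligibility) sets the composition of the sample: "Specific variables for which we will target sampling include: gender (~50% female), age", followed by occupation. Under Recruitment, "We will enumerate a list of current RCCS participants with key demographics". The parent cohort is described in Section 4 as holding more than 20 "years of data on HIV prevalence/incidence, health behaviors, sexual networks". In Table 1 the condom question ("If so, did you use condoms") is asked only after a yes to sex outside a marital or long-term partnership.

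**The concern.** The plan promises estimates for three behavioural areas but gives numbers for one. For a yes/no outcome, relative precision depends on how many people have the behaviour, and 50% is a comfortable rate. Nothing in the text shows that smoking or non-marital sex is as common, and no sampling target makes it so. The planned contrast is change from each participant's own Days 1-30 baseline. On a relative scale, someone who never reports a behaviour tells us little about its reduction. Condom use has a smaller base still.

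At stake is the pilot's own stated product. If few recruits have a behaviour, the estimate for it could fall almost anywhere, yet the Abstract intends these estimates to inform later large trials.

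**Working it through.** **Inputs.** 120 participants (Section 4, Eligibility) randomised 1:1 (Section 4, Follow-up Days 31-90) give 60 per arm. The alcohol rate is 50% (Section 7). Two-sided 0.05 and no loss are not stated; they are inferred because they reproduce Table 3. Every other prevalence below is an assumption.

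**Step 1: reproduce Table 3.** Pooled two-proportion test with d = p1 - p2, p̄ = (p1 + p2)/2, s0 = √(2p̄(1-p̄)/60) and s1 = √((p1(1-p1) + p2(1-p2))/60):

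power = Φ((d - 1.96 s0)/s1) + Φ((-d - 1.96 s0)/s1)

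For 0.50 v 0.25: s0 = 0.0884, s1 = 0.0854, and (0.25 - 0.1732)/0.0854 = 0.90, so power is 0.816. The four rows come to 0.195, 0.382, 0.611 and 0.816, each within 0.001 of the printed value. Table 3 is correct.

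**Step 2: a halving from other assumed prevalences p.** Same power formula. Expected 95% interval for the ratio: 0.5 ×/÷ exp(1.96 √((1-p)/(60p) + (1-p/2)/(30p))). At p = 10% the root is √(0.150 + 0.317) = 0.683 and the factor is exp(1.339) = 3.81.

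| Assumed p | Expected per arm | Power | Interval for ratio |
|---|---|---|---|
| 5% | 3 | 0.11 | 0.07-3.44 |
| 10% | 6 | 0.18 | 0.13-1.91 |
| 20% | 12 | 0.33 | 0.20-1.25 |
| 30% | 18 | 0.50 | 0.24-1.02 |
| 50% | 30 | 0.82 | 0.30-0.83 |

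With Binomial(60, p) per arm, the chance that at least one arm holds 2 or fewer people with the behaviour is 0.66 at 5%, 0.10 at 10% and 0.0004 at 20%.

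**Step 3: allow for repeated answers.** Step 2 treats each person as one yes/no, whereas Section 7 plans mixed models on repeated reports with a personal baseline. A simulation of 60 per arm, with 30 baseline and 60 follow-up daily answers, full response and a halving of daily probabilities, compared the pooled follow-up-to-baseline ratio between arms. It assumed mean daily frequencies of 0.1 to 0.7 among those with the behaviour and person-level log-change SDs of 0.5 to 1.0. The middle 95% of estimates was:

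- at 10% prevalence, 0.31-1.03 (most favourable setting) to 0.05-4.11 (least favourable);
- at 30% prevalence, 0.43-0.79 to 0.18-1.76.

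At 5%, between 9% and 41% of simulated trials gave no estimate because a count was zero.

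Two limits apply. First, the favourable results centre near 0.57, not 0.5 (√(0.31 × 1.03) = 0.57), because daily probabilities are capped at 1. With the simulated log SD of 0.301, a range centred on 0.5 would be 0.5 ×/÷ exp(1.96 × 0.301), or 0.28 to 0.90. Second, a pooled ratio of ratios is not the planned mixed model, and the failures to produce an estimate belong to that ratio.

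**Step 4: the same question as a difference.** Section 7's own example is a change in the proportion of yes responses. For a simple difference in proportions after a halving, the 95% half-width is 1.96 s1: 0.094 at 10% prevalence and 0.167 at 50%. The difference can be computed whatever the counts, though it is also smaller: 0.05 against 0.25.

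**The case for a change.** The strongest case for a change is that the exploratory label does not settle the matter. Section 7 disclaims efficacy power but still names preliminary effect estimates as the aim, and repeated answers from few people cannot replace more people. Going from 10% to 30% prevalence at the same N cuts the simulated SD of the log estimate by roughly half (0.301 to 0.158 in the favourable setting). The cohort already records health behaviours and the sample is already purposive, so a behavioural minimum would need no extra participants. At the least, a sentence could restrict sparse outcomes to description.

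The facts in this stand: only alcohol is quantified, no target is behavioural, and rarity would cost precision. What does not follow is that the plan is faulty. Power and whether an interval crosses 1 are efficacy criteria; by them the plan's own alcohol example reaches only 0.195 to 0.611 for reductions of 20 to 40%, and the plan openly accepts that. A minimum share, say 30%, has no basis in the documents. It would cut against the broad range of participants that Eligibility seeks for generalisability. It would also mean choosing people by their answers on smoking and sex, with IRB agreement, in a study whose Risks section puts loss of confidentiality first. Condom use would remain conditional on a reported event even then.

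**Conclusion.** No change is needed. This is partly missing detail that analysts will supply and partly a fair trade-off. The plan claims no power or precision for smoking, diet or sexual behaviour, so there is no stated figure that it fails to meet. The Days 1-30 data will show how many participants report each behaviour, and the interval around each estimate will show how little a sparse one can support. Anyone designing a later trial would see both. Listing parent-cohort prevalences and expected interval widths would make Section 7 fuller, but would not alter the sample, the analysis or an honest reading of the results.

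The possible imprecision is real but conditional. At an assumed 5 to 10% prevalence (3 to 6 people per arm), an estimate of relative change would be of little use for planning. At 30%, under favourable assumptions about repeated answers, it would be reasonably informative (0.43 to 0.79). At the alcohol rate of 50% the problem does not arise. The documents do not say where smoking or non-marital sex falls in that range, and the simulated figures rest on assumed reporting frequencies and a simpler contrast than the planned model.
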